11.1.5 Columbia-Suicide Severity Rating Scale (C-SSRS)

The Columbia-Suicide Severity Rating Scale (C-SSRS)¹⁶ is a systematically administered instrument developed to track suicidal adverse events across a treatment study. The instrument is designed to assess suicidal behavior and ideation, track and assess all suicidal events, as well as the lethality of attempts. Additional features assessed include frequency, duration, controllability, reason for ideation, and deterrents. The C-SSRS is considered a low-burden instrument, as it takes less than 5 minutes to administer. Raters will receive instruction on the administration of the C-SSRS assessment scales prior to administration of the scales. The C-SSRS will be administered at the times outlined in [Table 2](#).

Subjects expressing suicidal ideation with plan, either by answering "yes" to questions 4 and/or 5 to the suicidal ideation portion of the C-SSRS or via clinical interview, will be evaluated immediately by the Investigator or another medically qualified individual (M.D., D.O.). The Medical Monitor must be notified and the subject will be discontinued from participation in the study. The subject will be referred for appropriate psychiatric follow-up treatment, if necessary, per the judgment of the Investigator or the medically qualified individual. The Medical Monitor will also be notified. In addition, if the subject expresses suicidal ideation or suicidal behavior at any time during the course of the study, the subject should be discontinued from participation in the study and referred for proper psychiatric follow-up care. The Investigator and the Medical Monitor should be notified immediately as well.

Under no circumstances should a subject who has positively endorsed or expressed suicidal ideation or behavior be left alone, be allowed to exit the site, or go home before a qualified medical professional has evaluated the subject's risk.

The "Already Enrolled Subjects" C-SSRS will be the first assessment scale administered to the subject. At each subsequent assessment, the "Since Last Visit" C-SSRS scale should be administered.

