If the subject has previously completed the "Already Enrolled Subjects" scale in the S187.3.003 study, the subject should complete the "Since Last Visit" scale at all scheduled time points outlined in [Table 2](#) in this study. For subjects with a C-SSRS completed at their S187.3.003 final visit, that S187.3.003 final visit C-SSRS assessment will be considered baseline for the S187.3.005 study. For all other subjects, the first C-SSRS assessment completed in this study will serve as baseline.

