Subject disposition will be summarized including the primary reason for premature discontinuations and a listing of all subjects not included in the safety population.

Descriptive statistics will be provided for demographics and baseline characteristics.

Concomitant medication use will be summarized over time.

Baseline and Endpoint

Unless noted otherwise, the baseline value for a variable is defined as the last non-missing value collected in the current study or the previous open-label LCIG study before the first dose of study drug in the current study.

The endpoint value for a variable is defined as the last non-missing value assigned to the treatment period in the current study for the subject. For subjects transferring to commercial product, the end of treatment in the current study will be the last dose of study drug. For subjects who are discontinuing LCIG treatment, the end of treatment in the current study will be the removal of the PEG-J tube.

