6.4.5 Baseline Period for Study 3005

The Baseline Period for Study 3005 is defined as the time before the first 3005 LCIG infusion. For efficacy measures, the final value in the previous study (Study 3003 or Study 3004) will be retrieved from the relevant database and will be considered the 3005 baseline value. For safety evaluations, the final assessment in the previous open-label LCIG study or in 3005 that is on or before the date of the first 3005 LCIG infusion will be used as the 3005 Baseline value. For systolic blood pressure, diastolic blood pressure and

pulse, the final assessment where results are present for both the supine and standing position will be considered baseline.

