8.5.5.5 Columbia Suicide Severity Rating Scale (C-SSRS)

The Columbia-Suicide Severity Rating Scale (C-SSRS)⁵ is a systematically administered instrument developed to track suicidal adverse events across a treatment study. It was added to the flowchart of study assessments (Appendix 12.1.3) with Protocol Amendment 3. At each study visit, the C-SSRS will collect experience since the last visit. The incidence of subjects with affirmative responses on the C-SSRS at any time during the Treatment Period will be provided.

Each summary will include the number and percentage of subjects with one or more affirmative responses to each of the 5 suicidal ideation questions, each of the 6 suicidal behavior questions, any of the 5 suicidal ideation questions, any of the 6 suicidal behavior questions, any suicidal ideation or behavior question, and the non-suicidal self-injurious behavior question.

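### For subjects first assessed after Day 1, the SAP counts the protocol-defined baseline C-SSRS as a Treatment Period response

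*SAP*

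**What the plan says.** **Protocol.** Section 11.1.5 sets a baseline rule for this scale alone. If a C-SSRS was completed at the end of Study 3003, "that S187.3.003 final visit C-SSRS assessment will be considered baseline for the S187.3.005 study". Otherwise, "For all other subjects, the first C-SSRS assessment completed in this study will serve as baseline". Footnote f of protocol Table 2 says the same. Neither place requires the first Study 3005 assessment to precede the first dose. The general baseline rule in protocol 13.3 leaves room for such an exception, since it opens: "Unless noted otherwise, the baseline value for a variable is defined as the last non-missing value collected in the current study". Section 11.1.5 also specifies two forms: an Already Enrolled Subjects form at the first assessment and a Since Last Visit form afterwards. Subjects who completed the first form in Study 3003 use only the second.

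**SAP.** On the scale's history, 8.5.5.5 says: "It was added to the flowchart of study assessments (Appendix 12.1.3) with Protocol Amendment 3". For safety evaluations, 6.4.5 takes as baseline the final assessment in the previous open-label study "or in 3005 that is on or before the date of the first 3005 LCIG infusion". Sections 6.4.6 and 6.4.8 assign Day 1 data to baseline and put later safety assessments, up to one day after last PEG-J exposure, in the Treatment Period. None of these sections has a C-SSRS exception. Section 8.5.5.5 describes the instrument thus: "At each study visit, the C-SSRS will collect experience since the last visit". The planned summary is: "The incidence of subjects with affirmative responses on the C-SSRS at any time during the Treatment Period will be provided". No baseline row is planned. Footnote f of the schedules in SAP 12.1.3 and 12.1.4 nevertheless reproduces the protocol's C-SSRS baseline rule. SAP 10.1, which lists departures from the protocol, does not mention the C-SSRS.

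**The concern.** The same assessment has two roles. For some subjects, the form that the protocol and the SAP appendix call baseline is, under the body of the SAP, an on-treatment observation that can make the subject a case. A programmer working from footnote f and one working from 6.4.5 to 6.4.8 would produce different tables.

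The C-SSRS is a named assessment under the protocol's secondary safety objective (6.2), and this is the only planned summary table for it. As specified, that table cannot show whether a subject was affirmative at the defined baseline, later, or both. The neighbouring summaries of sleep attacks (8.5.5.3) and the MIDI (8.5.5.4) do report baseline and Treatment Period separately.

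**Working it through.** The documents give no event rate or sample-size figure for the C-SSRS, so there is no figure to reproduce. The check traces each type of subject through both sets of rules, then does the count arithmetic.

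**Tracing the rules**

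| Subject | Protocol 11.1.5 and SAP footnote f | SAP 6.4.5, 6.4.6, 6.4.8 | Result |
|---|---|---|---|
| 1. C-SSRS at Study 3003 final visit | That form is baseline | Before Day 1, so baseline | Agree |
| 2. No such form; first 3005 C-SSRS on or before Day 1 | First 3005 form is baseline | Baseline Period | Agree |
| 3. No such form; first 3005 C-SSRS on Day 2 or later | First 3005 form is baseline | Treatment Period (Month 6 window is Days 2 to 270) | Conflict |

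Only group 3 is affected. It was foreseeable: the schedules for Amendments 1 and 2 (SAP 12.1.1 and 12.1.2) contain no C-SSRS, so a subject already on Study 3005 treatment when Amendment 3 took effect, and without a Study 3003 final-visit form, is in group 3. Its size is not given.

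**Effect on the count.** Let

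- a = subjects affirmative on a protocol-baseline form dated after Day 1 and on no later form;
- b = subjects affirmative on a later, post-baseline form;
- N = subjects with any Treatment Period C-SSRS;
- m = those among N with no post-baseline form.

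The SAP counts a + b. The count consistent with the protocol baseline is b. The excess is a, which is zero or more, so the count can be too high but not too low.

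**Effect on the percentage.** The SAP rate is (a + b)/N.

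- With the denominator kept at N, the rate under the protocol baseline is b/N, and the excess is 100a/N percentage points.
- With the denominator limited to subjects having a post-baseline form, the rate is b/(N − m). The SAP rate exceeds it only if (a + b)(N − m) > bN, that is, if a(N − m) > bm.

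For illustration, take N = 275, the planned enrolment. This assumes that every subject contributes a Treatment Period form. The values of a, b and m are also assumptions.

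| a | b | m | SAP (a + b)/N | b/N | b/(N − m) |
|---|---|---|---|---|---|
| 0 | 3 | 0 | 3/275 = 1.09% | 1.09% | 1.09% |
| 1 | 3 | 0 | 4/275 = 1.45% | 1.09% | 1.09% |
| 5 | 3 | 0 | 8/275 = 2.91% | 1.09% | 1.09% |
| 10 | 3 | 0 | 13/275 = 4.73% | 1.09% | 1.09% |
| 1 | 10 | 60 | 11/275 = 4.00% | 3.64% | 10/215 = 4.65% |

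In the last row a(N − m) = 215 and bm = 600, so the SAP percentage is the lower one. The sign of the percentage error therefore depends on the denominator. Section 8.5.5.5 gives none: SAP 6.1 defaults to subjects with non-missing data, and the table list labels this table only as Safety Sample.

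**The case against.** The best defence is that counting every affirmative answer after Day 1 is the cautious choice for a safety scale. Subjects in group 3 were on LCIG when they completed the first form, so an affirmative answer may be a real on-treatment event. Protocol 11.1.5 also says that a subject expressing suicidal ideation or behaviour should be discontinued, so someone affirmative on the first form may have no later one. Restricting the summary to later forms could remove that event from the table. This stands, and it rules out simply discarding the first forms.

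It is also fair that the missing baseline row is not itself a departure from the protocol. Protocol 13.3 asks for the MIDI at baseline and during treatment but only for a summary of the C-SSRS. Listing QSL010 gives responses by subject and visit, so the information is recoverable, though not from the table.

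A reader might go further and infer that pre-existing ideation is being attributed to LCIG. The documents do not support that. They do not state the recall period of the Already Enrolled Subjects form, and the Study 3005 baseline is itself on LCIG, so it cannot separate events before LCIG from events on it.

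None of this removes the contradiction between the SAP's body and its own footnote f.

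**Conclusion.** The SAP is wrong as written for group 3: it treats the protocol-defined C-SSRS baseline as a Treatment Period response, against protocol 11.1.5 and its own schedules, without declaring a change. The number of subjects with affirmative on-treatment responses therefore mixes baseline and post-baseline responses and can be too high, never too low. The excess equals the number of group 3 subjects affirmative on the first form and on no later one. That number is not in the documents and may be zero.

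Two stronger conclusions might be drawn, and neither holds. One is that everyone without a Study 3003 final-visit form, including everyone from Study 3004, is affected. A first form on or before Day 1 is baseline under both rules, and Table 2 schedules a C-SSRS at baseline. The other is that the reported percentage is overstated by some assumed prevalence on first forms. Adding such a prevalence in full would require all subjects to be in group 3 with no overlap between first-form and later responders, and the undefined denominator leaves even the direction open.

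The conclusion rests only on the written rules. The percentages above are illustrative.

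**What to change.** 1. In SAP 6.4.5 and 8.5.5.5, state the C-SSRS baseline as in protocol 11.1.5: the Study 3003 final-visit assessment if there is one, otherwise the first assessment in Study 3005. Define it by order of assessment, not by form type, because a subject who completed the first form in Study 3003 but has no final-visit C-SSRS there will have a Since Last Visit form as baseline.
2. Correct the 8.5.5.5 sentence that describes every form as covering the time since the last visit.
3. In the C-SSRS table (14.3__7.3), show (a) baseline responses, with first forms dated after Day 1 on their own row so that no on-treatment event is lost, and (b) responses on later Since Last Visit forms.
4. State the denominator for (b) as subjects with at least one post-baseline form. The any-time total can stay as a further row.

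The cost is SAP wording and extra table rows. No new assessments or data collection are needed.

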8.5.5.6 Melanoma Check

A comprehensive assessment for the presence of melanoma must be performed at least once a year by a dermatologist experienced with the diagnosis of the condition. If a suspicious lesion is present, a biopsy should be obtained for proper diagnosis. Subjects who have a melanoma present at the start of the study, or who develop one during the course of the study should be discontinued from participation and referred for proper follow-up care.

8.5.5.7 Neurological Examination

At each of the scheduled visits indicated in the flowchart of study assessments a neurological examination will be performed including light touch and pinprick sensation, vibratory sensation, deep tendon reflexes, and strength assessments. Any abnormalities or symptoms identified will be reported as adverse events.

9.0 Statistical Analysis

This section will indicate how the statistical analysis will be performed on the basis of the conventions, definitions and techniques that are described in Section 6.0 through Section 8.0. To each standard table (T), listing (L) or figure (F) a unique code is assigned which is used as a reference in the SAP and indicated on the appropriate table/listing/figure template. For example, a demographics table is assigned the unique code of DMT001, where DM refers to the clinical domain (Demographic Data), T indicates that it is a table and 001 indicates that it is the first table in the DM set of tables. Tables, listings and figures that are referred to are listed in the Appendices, Section 12.2 and Section 12.3.

9.1 Subject Disposition

Subject disposition (DS) will be summarized for all centers/countries combined by means of the default summary statistics described in Section 6.0 (General Definitions, Methods, Naming Conventions and Data Handling).

Subject Samples:	Tables	All subjects consented and Efficacy Sample US Subset
	Listings	All subjects consented
	Figures	Not applicable
Subgroups:		Not applicable
Abbreviation:		DS

Standard Presentations

- DST001 The primary reason for premature discontinuation after consent, as recorded on the "Study Termination" form, will be presented. The primary reason for premature discontinuation includes:
- Adverse Event
 - Lack of Efficacy
 - Lost to Follow-up
 - Withdrew Consent
 - Administrative
 - Protocol Violation

The number of subjects who have completed the study and the number whose participation in the study is ongoing will also be presented. The percentage of subjects will be calculated relative to the number of consenting subjects.

- DST002 Subject validity/subject sample status will be summarized with the reason for exclusion from the Safety sample. The only reason for exclusion from the safety sample will be that the subject did not infuse any study medication after providing informed consent.
- DST003 The number and percentage of subjects prematurely discontinuing in each 3005 treatment year will be summarized.

Standard subject data listings include:

- DSL001 A listing of subjects who prematurely discontinued their participation in the study prior to receiving 3005 LCIG.

DSL002 A listing of subjects who discontinued participation after receiving 3005 LCIG will be presented. The relative treatment day of last contact with the subject and the last day of 3005 LCIG infusion, as captured on the "Study Termination" CRF form will be calculated as:

- Relative Treatment Day of Last Contact = (Date of Last Contact – Date of First 3005 LCIG Infusion) + 1
- Relative Treatment Day of Last 3005 LCIG Infusion = (Date of Last 3005 LCIG Infusion – Date of First 3005 LCIG Infusion) + 1

DSL003 Exclusion from the Safety subject sample together with the reason(s) for exclusion will be presented. This listing will include all possible reasons for exclusion per subject.

Study Specific Presentations

Not applicable.

9.2 Major Protocol Deviations

Major protocol deviations (DV) will be summarized for all centers/countries combined.

Subject Samples:	Tables	Safety sample
	Listings	All subjects consented
	Figures	Not applicable
Subgroups:		Not applicable
Abbreviation:		DV

Standard Presentations

DVT001 The number of unique subjects presenting with at least one major protocol deviation will be presented. In addition, the number and percentage of subjects allocated to treatment in each major protocol deviation category will be presented. Subjects may have more than one major protocol deviation.

Standard subject data listings include:

- DVL001 A by-subject listing of all subjects with one or more major protocol deviations will be presented.

Study Specific Presentations

Not applicable.

9.3 Inclusion/Exclusion Criteria

Only the exceptions are to be listed, that is, subjects with a response to the Inclusion Criteria of "No" and/or subjects with a response to the Exclusion Criteria of "Yes." Subjects with a missing response to Inclusion/Exclusion Criteria will also be presented.

Subject Samples:	Tables	Not applicable
	Listings	All subjects consented
	Figures	Not applicable
Subgroups:		Not applicable
Abbreviation:		IE

Standard Presentations

The response (Yes/No) per subject with at least one exception to each of the study specific inclusion/exclusion criteria, will be presented as a subject data listing as follows:

- IEL001 Listing of all Inclusion Criteria including a text description of each criterion and the response as either "Yes" or "No" for those subjects with at least one exception.
- IEL002 Listing of all Exclusion Criteria including a text description of each criterion and the response as either "Yes" or "No" for those subjects with at least one exception.

Study Specific Presentations

Not applicable.

9.4 Demographic Data and Other Baseline Characteristics

9.4.1 Demographic Data

Subject demographic data (DM), described below, will be summarized and presented for observed data only. All missing data will be presented as part of a missing category, if appropriate.

Subject Samples:	Tables	Safety sample and US Subset
	Listings	All subjects consented
	Figures	Not applicable
Subgroups:		Not applicable
Abbreviation:		DM

Standard Presentations

- DMT001 Qualitative demographic data, presented by means of default summary statistics, includes:
- Gender: Male or Female.
 - Race: American Indian or Alaska Native, Asian, Black of African Heritage or African American, Native Hawaiian or Other Pacific Islander, White. For each subject one or more race categories can be selected.
 - Ethnicity: Hispanic or Non-Hispanic.
 - Age: < 65 , ≥ 65 .
 - Country

Quantitative demographic data includes:

- Age (years) presented by default summary statistics.

Standard subject data listings include:

DML001 Standard demographic data will be presented. Missing data will not be imputed for the listing. An incomplete date will be presented, for example, as – Jan 1980, as originally entered in the CRF. The relative day of assessment will be calculated relative to the start of the 3005 LCIG infusion (RFSTDTN) and will be presented for those subjects who received 3005 LCIG infusion.

Study Specific Presentations

Not applicable.

9.4.2 Other Baseline Characteristics

Default summary statistics, described in Section 6.0 (General Definitions, Methods, Naming Conventions and Data Handling), of the baseline subject characteristics will be presented for all countries/centers combined.

Subject Samples:	Tables	Safety sample and US Subset
	Listings	All subjects consented
	Figures	Not applicable
Subgroups:		Not applicable
Abbreviation:		SC

Standard Presentations

- SCT001 Other subject characteristics (SC) include the following vital signs:
- Systolic Blood Pressure (SBP [mmHg]), supine, standing, and orthostatic
 - Diastolic Blood Pressure (DBP [mmHg]), supine, standing, and orthostatic
 - Pulse rate (bpm), supine, standing, and orthostatic
 - Height (m)
 - Weight (kg), overall and by gender
 - BMI (kg/m²)
 - Body temperature (degrees Celsius)
 - Route of measurement

Standard subject data listings include:

- SCL001 The aforementioned vital signs data will be presented by subject. The relative day of the assessment will be calculated relative to the start of 3005 LCIG infusion (RFSTDTN) and will be presented for those subjects who received 3005 LCIG infusion.

Study Specific Presentations

- SCT002 Other subject characteristics include the following assessments collected during the Initial Screening Period:
- Duration in years since the first diagnosis of PD
 - Diagnosis of bradykinesia (slowness of initiation of voluntary movement with progressive reduction in speed and amplitude of repetitive actions)
 - Diagnosis of muscular rigidity
 - Diagnosis of 4 – 6 Hz resting tremor
 - Diagnosis of postural instability not caused by primary visual, vestibular, cerebellar or proprioceptive dysfunction

SCT003 PD medications that were started during the previous study and continue to be used by the subject will be summarized. The primary ATC class (e.g., Dopa and Dopa Derivatives, Dopamine Agonists, COMT Inhibitors, etc.) will be used to group similar medications. Subjects will be categorized according to the number of medication classes used (i.e., 1, 2, 3, or > 3 PD medication classes). Within each group of subjects, the number of subjects using each medication type will be summarized using default summary statistics. The percentage of subjects taking 1, 2, 3, or > 3 PD medications is calculated relative to the total number of subjects considered valid for the specific subject sample, that is, Safety subject sample. The percentage of subjects taking a medication in a specific ATC class is calculated relative to the number of subjects in the 1, 2, 3, > 3 PD medication subgroups.

Study Specific subject data listings include:

- SCL002 A listing of the date and duration of diagnosis as well as results of the 'Diagnosis of Idiopathic Parkinson's Disease' according to the modified UKPDS brain bank criteria will be provided.
- SCL003 By-subject and within-subject by ascending start date/relative start day of PD medication use. In SCL003 the relative start and stop day of PD medication use will be calculated relative to the first 3005 LCIG infusion and will be presented for those subjects who were allocated to treatment and received at least one dose of investigational study medication. If the medication is "Ongoing" it will be indicated as such in the listing and the relative stop day will not be calculated. Only original dates will be presented in the listing even though the relative day may be based on an imputed date.
- SCL004 A listing of the relevant WHO-DD coding information, sorted in the same way as SCL003 will also be provided.

